### 9.4.3. *Electrocardiograms*

For each subject, 12-lead ECGs will be obtained according to the Schedule of Activities (Section 2). ECGs must be recorded before collecting any blood for safety or PK tests. Subjects must be supine for at least 5 minutes before ECG collection and remain supine but awake during ECG collection.

ECGs may be obtained at additional times, when deemed clinically necessary. Collection of additional ECGs at a particular time point is allowed to ensure high-quality records. All ECGs recorded should be stored at the investigational site. The timing of the ECG collections may be adjusted after a review of the PK data.

At screening and final discharge/early discontinuation, a single ECG will be obtained and does not need to be transmitted to the ECG vendor. The screening ECG will be interpreted by the investigator or qualified designee at the site to determine whether the subject meets entry criteria.

For the predose ECG measurement of each period in Parts A and C (but not Part B), 3 sets of triplicate ECGs will be obtained approximately 10 minutes apart. For Part B, predose ECG measurements will be single.

For Parts A and C, after study entry, ECGs will be obtained in triplicate at approximately 1-minute intervals at each ECG time point. At least 1 ECG in each triplicate set will be interpreted by the investigator or qualified designee at the site as soon as possible after the time of ECG collection, and ideally while the subject is still present, for immediate subject management.

For Part B, at each time point, a single ECG will be collected and subsequently interpreted by the investigator or qualified designee in the same way as above.

If at any time a clinically significant increase in the QTc interval is present or the ECG shows a clinically important change, then the investigator should assess if the subject can continue in the study. Any clinically significant findings that result in a diagnosis should be recorded on the CRF. Any clinically significant findings that do not result in a diagnosis should be commented on and appropriately documented. If a clinically significant change is seen, additional ECGs may be obtained at appropriate intervals until readings return to within normal levels. In addition, a 12-lead Holter recording may be initiated in an individual subject with a clinically significant ECG abnormality. In these cases, digital recordings of continuous ECG recordings will be transferred to a central ECG laboratory designated by Lilly. The ECG laboratory will perform quality control checks for the time points of interest (eg, acquisition quality for ability to measure/interpret demographics and study details). The ECG laboratory will then store the recording and a cardiologist at the central ECG laboratory may conduct a full over-read on extracted ECG time points of interest. No reports will be issued from the central ECG laboratory back to the sites for any ECGs. All data from the ECG over-reads and measured intervals will be placed in a Lilly database for analytical and study report purposes. Any new clinically relevant finding should be reported as an AE.

The ECGs will subsequently be electronically transmitted to the centralized ECG vendor designated by Lilly for storage. The automated ECG parameters will be used for data analysis

and report-writing purposes. ECGs may be overread by a medically qualified professional (eg, cardiologist) to assess clinically significant findings on the automated ECG readings, should these occur.

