### 9.2. Adverse Events

Investigators are responsible for monitoring the safety of subjects who have entered this study and for alerting Lilly or its designee to any event that seems unusual, even if this event may be considered an unanticipated benefit to the subject.

The investigator is responsible for the appropriate medical care of subjects during the study.

The investigator remains responsible for following, through an appropriate health care option, AEs that are serious or otherwise medically important, considered related to the investigational product or the study, or that caused the subject to discontinue the investigational product before completing the study. The subject should be followed until the event resolves, stabilizes with appropriate diagnostic evaluation, or is reasonably explained. The frequency of follow-up evaluations of the AE is left to the discretion of the investigator.

After the informed consent form is signed, study site personnel will record, via CRF, the occurrence and nature of each subject's preexisting conditions. Additionally, site personnel will record any change in the condition(s) and the occurrence and nature of any AEs.

The investigator will interpret and document whether or not an AE has a reasonable possibility of being related to study treatment, or a study procedure, taking into account the disease, concomitant treatment, or pathologies.

A "reasonable possibility" means that there is a cause and effect relationship between the investigational product, study device, and/or study procedure and the AE.

Planned surgeries should not be reported as AEs unless the underlying medical condition has worsened during the course of the study.

If a subject's investigational product is discontinued as a result of an AE, study site personnel must report this to Lilly or its designee via CRF.

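### Section 9.4.3 gives a finding made only at central over-read of a Holter recording no stated route to the investigator, yet requires new findings to be reported as AEs

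*Protocol*

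**What the plan says.** Protocol Section 9.4.3 covers what happens after an important ECG change.

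- When such a change is present, "the investigator should assess if the subject can continue in the study".
- The protocol also offers continuous monitoring as an option: "a 12-lead Holter recording may be initiated in an individual subject with a clinically significant ECG abnormality". The file then goes to a central laboratory chosen by the sponsor.
- That laboratory checks quality and keeps the file. Expert reading there is optional: "a cardiologist at the central ECG laboratory may conduct a full over-read on extracted ECG time points of interest".
- The rule on feedback is categorical: "No reports will be issued from the central ECG laboratory back to the sites for any ECGs". The sentence makes no exception for urgent or significant findings. Over-read data go to a sponsor database, for analysis and the study report.
- The paragraph ends: "Any new clinically relevant finding should be reported as an AE". It does not say by whom.

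Section 9.2 assigns AE recording to site personnel, through the CRF, and adds: "The investigator will interpret and document whether or not an AE has a reasonable possibility of being related to study treatment".

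For scheduled tracings in Parts A and C, Section 9.4.3 states: "At least 1 ECG in each triplicate set will be interpreted by the investigator or qualified designee at the site". In Part B the single ECG at each time point is read in the same way.

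**The concern.** The paragraph asks for new clinically relevant findings to become AEs, but the only reader it describes for the Holter may not report to the people who record AEs. If the over-read shows something beyond the abnormality that prompted the recording, the text does not say how the investigator learns of it.

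Three things would be at stake.

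- **Primary endpoint.** Incidence of TEAEs is the primary endpoint (Protocol Section 4). SAP Section 6.8.2.1 builds TEAEs from reported AEs, so a finding that no one at the site reports is not counted.
- **Relatedness and continuation.** Both judgements belong to the investigator. Stopping criteria 1 to 3 in Section 7.4.1 count events considered related to LY3323795, and that section has the investigator assess safety data independently.
- **Cardiac signal.** Section 3.2 reports peak QTc changes of +7 and +31 msec and peak heart-rate changes of -15 and -39 bpm in dogs at 5 and 120 mg/kg. Table SCAA.2 gives a Cmax multiple of 5 between the QTc effect level in dogs and the projected human exposure at 100 mg. Part A subjects return for later periods in which the planned dose in their cohort is ten times higher (0.3, 3, 30 mg; 1, 10, 100 mg).

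**Working it through.** The plan states no figure on this point, so the check follows a finding made only at central over-read through the text.

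1. **Start.** The investigator sees a clinically significant abnormality on a 12-lead ECG and may start a Holter (9.4.3). The triggering abnormality is known at the site.
2. **Reading.** The recording goes to the central laboratory. A cardiologist there may over-read extracted time points. No site reading of the Holter is described; the on-site reading rule in 9.4.3 concerns the 12-lead ECGs.
3. **Direct route to the site.** Closed, because the laboratory issues no reports to sites for any ECG.
4. **Route through the sponsor.** The over-read data reach a sponsor database. Two general channels follow:
   - Section 9.4.5: the sponsor's clinical pharmacologist monitors safety data throughout. No step passes over-read results to the site.
   - Section 5.1.1.1: investigator and sponsor both assess safety data, ECGs included, before each escalation. Over-reads are not named or required to be available, and the review serves Part A escalation only.
5. **Recording.** Section 9.4.3 wants the finding reported as an AE; Section 9.2 puts that task at the site.
6. **Analysis.** SAP Section 6.8.2.5 covers QTc plots and frequency tables and mentions neither Holter recordings nor over-reads, so the SAP supplies no second place where the finding would be picked up.

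Steps 3 to 5 do not join up: the task sits at the site, the information sits with the laboratory and the sponsor, and no sentence connects them.

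**Size if it happened once.** Suppose one subject on active drug had such a finding and it went unrecorded. The incidence of that event term at that dose would be understated by 1/6 = 16.7 percentage points in Part A (6 on active drug per dose level) or 1/5 = 20 points in Part B (5 per dose). This illustrates one event; it is not an estimate of how often it would occur.

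**The case against.** The strongest reply is that the event is rare and conditional. A Holter is optional and follows an abnormality that the investigator already knows of, must assess, and may follow with further ECGs until readings return to normal. The over-read is also optional and limited to selected time points. All of this stands, and it confines the point to additional findings in an optional read.

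Second, the rule stops reports from the laboratory; it does not stop the sponsor from telling the investigator. Part A doses in one subject are at least 14 days apart, which leaves time for that. This stands too. A reader might infer that such a finding cannot reach the investigator, but the documents support only that no route is specified. Leaving relay to informal contact is a weak substitute, because the sponsor team is unblinded (Sections 7.3 and 10.3.5) and a written route can exclude treatment information.

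Third, the AE sentence could be read as covering only what the site itself sees. On that reading the contradiction softens, but a finding made only centrally then has no stated path to becoming an AE, so the gap remains.

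Two further inferences fail. One is that scheduled triplicate ECGs without a required site interpretation measure the problem. At least one tracing in each set is read on site, the others are replicates about 1 minute apart, and none is a Holter. The other is that QTc prolongation in general could escape the stopping rules. Criterion 5 in Section 7.4.1 is numerical, uses the mean of three readings and needs no relatedness judgement. Criterion 4 is ophthalmic and has no bearing here.

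**Conclusion.** The concern holds in a limited form. Section 9.4.3 bars reports from the central laboratory to the sites for any ECG, and the same paragraph requires new clinically relevant findings to be reported as AEs, a task that Section 9.2 gives to the site. With no site reading of the Holter and no relay step described, an additional finding made only at central over-read has no specified route to the investigator and could be missing from the TEAE count.

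The frequency cannot be stated: the documents give no expected number of Holter recordings or over-reads, and it may be zero. The conclusion assumes that no relay procedure exists in a document outside the protocol and SAP, such as the ECG vendor specification. If one exists, the protocol should refer to it. This is a cheap improvement to a safety communication path, not a flaw in the design or the analysis.

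**What to change.** Reconcile the sentences in Section 9.4.3 on central reports, AE reporting and the investigator's assessment:

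- Limit the no-report rule to routine reports.
- State that a clinically relevant finding made only at central over-read is passed to the investigator without treatment information.
- Name the role that passes it on and the role that records it as an AE where applicable.

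The sponsor should settle the timing, since the over-read is optional and has no stated turnaround; a fixed deadline could make it time-critical.

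The cost is a short text change in Section 9.4.3, an added step in the ECG vendor specification, and occasional alerts to the site. The change adds no ECGs and touches no dose, ECG threshold or stopping criterion.

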#### 9.4.4. Other Tests

##### 9.4.4.1. Neurological Survey

A directed neurological survey will be performed by a physician, nurse practitioner, or physician's assistant according to the Schedule of Activities (Section 2). If abnormalities are noted, additional examinations should be performed at daily intervals until the subject's test scores have returned to baseline levels. The examiner should be familiar with the subject's baseline survey and may examine the subject prior to dosing as needed. Mandated elements of the survey include inspection for tremor, extraocular movements, brachial and patellar deep tendon reflexes, finger-nose pointing, and Romberg sign.

Table SCAA.4 presents how the findings of the neurological survey will be scored. For subjects with mild (1+) tremor or nystagmus at baseline, increases in these findings should not be scored at a higher level unless the examiner judges them to be significantly exacerbated compared with baseline. Other elements of the physical examination may be included on an optional or symptom-directed basis.

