**Table SCAA.4. Scoring of Neurological Surveys**

Score	0	1	2	3	4
Tremor, nonspecific location	Absent	Visible with limb extension and/or careful inspection	Visible without limb extension	Interferes with motor function	
Nystagmus, nonspecific location	Absent	1-3 beats on lateral gaze	>3 beats on lateral gaze	Present on forward gaze	
Reflex test, nonspecific location	Absent	Trace	Normal	Increased	Clonic
Finger-nose	Normal	Abnormal			
Romberg sign	Absent	Present			

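### In subjects with a mild baseline tremor or nystagmus, an undefined examiner judgement can hold the neurological survey score below the level that Table SCAA.4 assigns to what was seen, and the observed level is not kept

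*Protocol*

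**What the plan says.** Table SCAA.4 in the Protocol scores five items. For tremor and nystagmus the levels are tied to what the examiner sees. Tremor scores 1 if it shows on limb extension or careful inspection, and 2 if "Visible without limb extension". Nystagmus scores 1 for one to three beats when looking sideways, and 2 for ">3 beats on lateral gaze".

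Section 9.4.4.1 then adds an exception for some subjects. Where tremor or nystagmus is already mild (1+) before dosing, a later rise "should not be scored at a higher level unless the examiner judges them to be significantly exacerbated compared with baseline". Neither document says what counts as significant. The exception covers increases only, and only tremor and nystagmus. Reflexes, finger-nose pointing, the Romberg sign, and subjects with any other baseline score follow the table.

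The same section governs extra surveys: "If abnormalities are noted, additional examinations should be performed at daily intervals until the subject's test scores have returned to baseline levels".

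The survey is used in two places. Section 5.1.1.1 lists it among the safety data reviewed before each Part A escalation. Section 10.3.1.2 includes CNS monitoring among the safety parameters to be listed and summarised descriptively.

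**The concern.** A score with an observable definition should mean the same thing in every subject. Under the exception it does not. Nystagmus of more than three beats is entered as 2 in a subject who started at 0, but may be entered as 1, the level defined as one to three beats, in a subject who started at 1. The entry then mixes two things: what was seen, and whether the examiner thought the change mattered.

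This is a first-in-human study of a drug intended to act in the brain, and Section 3.2 reports CNS activity in one dog at the highest dose. The survey is the study's dedicated CNS examination. With six active subjects per dose level in Part A, a single shift is a visible part of the data at that dose. The protocol specifies only one score per item and does not ask for the observed level anywhere else, so a held-down score cannot be undone at the analysis stage.

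**Working it through.** The plan attaches no sample size, power or event rate to the survey, so there is no planned figure to reproduce. The check is a reading of the passages against each other, followed by a rough sizing.

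**Step 1. What is entered for a subject with baseline score 1 (Section 9.4.4.1 and Table SCAA.4)**

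| Finding after dosing | Judged significantly worse? | Score entered | Change shown |
|---|---|---|---|
| Meets the definition of 2 | Yes | 2 | +1 |
| Meets the definition of 2 | No | 1 | 0 |
| Still meets the definition of 1 | Not relevant | 1 | 0 |
| Absent | Not relevant | 0 | -1 |

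The second and third rows give identical data. That is the loss of information. A move from 1 to 3 is formally covered too, but score 3 means tremor that impairs motor function or nystagmus on looking straight ahead. An examiner is unlikely to call that insignificant, so the realistic case is the shift from 1 to 2.

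**Step 2. Effect on a comparison.** Suppose that, among subjects starting at 1, a proportion *d* on drug and *p* on placebo cross into 2, and a fraction *s* of those crossings is held at 1 in both groups. The entered difference is (1 - *s*)*d* - (1 - *s*)*p* = (1 - *s*)(*d* - *p*). A real difference in this subgroup shrinks by the fraction *s*. The documents give no value for *s*, *d* or *p*.

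**Step 3. How many subjects.** The proportion starting at 1+ is not given. Assume 5% to 20%, for illustration only.
- Part A in total (18 completers planned): 18 × 0.05 = 0.9 to 18 × 0.20 = 3.6, so about 1 to 4 subjects.
- Active subjects at one dose level (6): 6 × 0.05 = 0.3 to 6 × 0.20 = 1.2.
- Chance that at least one of those 6 starts at 1+: 1 - 0.95^6 = 26% to 1 - 0.80^6 = 74%.
- One held shift: 1/6 = 16.7 percentage points of the active subjects at that dose.

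The last figure is conditional. The subject must start at 1+, cross into 2 and be judged not significantly worse. Neither document defines an incidence of worsening on the survey.

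**Step 4. Trigger and stop for extra surveys.** They start when an abnormality is noted and end when scores are back at baseline. A subject held at 1 has a noted finding, which may start them, and a score already at baseline, which meets the stop. The text does not say which governs.

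**Step 5. What does not depend on the score.** Section 9.2 has site staff record any change in a preexisting condition and any adverse event. The treatment-emergent definition (Protocol Appendix 1, SAP Section 6.8.2.1) includes worsening from the pretreatment state. The primary endpoint is the incidence of such events (Section 4). None of the five numbered stopping scenarios in Section 7.4.1 uses a survey score.

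**The case against.** The case for leaving the sentence alone is substantial. The rule limits a score and does not forbid recording. Worsening judged significant is scored. Mild tremor or a few beats of nystagmus can fluctuate, and an examiner who knows the subject's baseline, as the section asks, is reasonably placed to filter noise. The examiner is blinded in Parts A and B, so the rule applies alike to drug and placebo. No inferential analysis of the survey is planned. Subjects are overtly healthy, and neurological disorders that pose a risk or interfere with interpretation are excluded, so few may start at 1+. That the rule has no counterpart for improvement matters little in a survey that looks for harm.

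Most of this stands, and it limits the point. A reader might infer that examiners are told not to record worsening, that real CNS worsening is therefore hidden, or that it triggers no follow-up survey. The documents do not support those readings. The exception lets significant worsening through, the adverse event route is separate, extra surveys start on a noted abnormality rather than a rise in score, and scheduled surveys continue regardless. Nor do the documents support a claim that the rule favours one treatment arm.

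Two things remain. Equal application under blinding prevents favouritism but not the shrinkage in Step 2. And adverse event reporting, which also rests on site judgement, is a second route to the information; it does not restore the survey score.

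**Conclusion.** The point holds in a limited form. An undefined judgement, acting on increases only, can override the scale's own definitions for tremor and nystagmus in subjects who start at 1. Increases that meet the definition of 2 but are not judged significant appear as no change in the escalation reviews and the CNS summaries. The cost is sensitivity, together with an observation that cannot be recovered from the survey data.

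The size cannot be fixed from the documents and is probably small. The figure of 1 to 4 Part A subjects rests entirely on the assumed 5% to 20% prevalence, and only some of those subjects would cross a boundary. The primary endpoint and the stopping scenarios are not compromised. This is an inexpensive improvement to data recording, not a flaw that threatens the study's conclusions. The mismatch between trigger and stop is an ambiguity in the text, not evidence that follow-up would be missed.

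**What to change.** Replace the exception in Section 9.4.4.1 with an instruction to enter the Table SCAA.4 score actually observed in every subject. Add a separate yes/no item recording whether, in the examiner's judgement, the finding is significantly exacerbated compared with baseline. List both. Section 10.3.1.2 already does this for eye assessments, where a change from baseline and its clinical significance are two separate items. The examiner's judgement is kept and no longer overwrites the observation.

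The sponsor should also reconcile, within Section 9.4.4.1, the start of extra surveys (an abnormality noted) with their end (scores back at baseline), so that it is clear what applies when a finding is noted but the score has not moved.

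The cost is one sentence, one case report form field, and a few more trivial shifts in the listings. Placebo subjects give some context for those shifts, but not much: three per dose level in Part A and two per cohort in Part B. Part C is open-label with no placebo, so there the judgement item has to carry the interpretation.

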**Table SCAA.4. Scoring of Neurological Surveys**

Score	0	1	2	3	4
Tremor, nonspecific location	Absent	Visible with limb extension and/or careful inspection	Visible without limb extension	Interferes with motor function	
Nystagmus, nonspecific location	Absent	1-3 beats on lateral gaze	>3 beats on lateral gaze	Present on forward gaze	
Reflex test, nonspecific location	Absent	Trace	Normal	Increased	Clonic
Finger-nose	Normal	Abnormal			
Romberg sign	Absent	Present			

